9.1.6 Definition of a non-interventional study

The study is a 'non-interventional study' as defined for drug studies in Directive 2001/20/EC (European Commission, 2001) with primary data collection and will follow the guidelines for Good Pharmacoepidemiology Practices (Public Policy Committee, 2016).

This means that:

- The medicinal product is prescribed in the usual manner in accordance with the terms of the marketing authorisation;
- The assignment of the patient to a particular therapeutic strategy is not decided in advance by a trial protocol but falls within current practice and the prescription of the medicine is clearly separated from the decision to include the patient in the study

- No additional diagnostic or monitoring procedures are applied to the patients. Interviews, questionnaires, blood samples and patient follow-up may be performed as part of normal clinical practice.
- Epidemiological methods are used for the analysis of collected data.

9.2 Setting

The study is planned to be conducted in approximatively 25 sites in 2 countries. Investigators will be clinical dermatologists. Each participating site is expected to include in average 5/6 patients. In case of slow recruitment in some sites, the other sites will be allowed to enrol up to 10 patients. Inclusion requires that Kyntheum® is prescribed in accordance with the approved terms of the marketing authorization in the country and that none of the stated contraindications apply.

Caution should be taken by the treating physician concerning any precautions, warnings and potential drug interactions stated in the product label.

Patients should be included in the study only once.

The study aims to involve sites and investigators that are representative for HCPs that prescribe biologics to patients suffering from *psoriasis vulgaris*. Sites can be hospital (university, private, public) dermatology departments, private dermatology clinics, and all sorts of general practices. Sites where patients are prescribed Kyntheum®, but for continuation of care are routinely referred to a different site without access to prescribe Kyntheum®, should not be selected for this study.

Information about the PSO-TARGET study should be given after the decision is made to treat the patient with Kyntheum®. It will be emphasized that the participation study will not condition the patient treatment and will not alter the visit schedule defined by the standard of care (3 and 12 months). After enrolment (i.e. signature of the Informed Consent Form), the physician will provide the patient with the QoL component grid along with the DLQI questionnaire. After having explained the purpose of the table in regards to the study, the physician shall give the patient enough time to reflect on which component is the most important for him/her without influencing him/her. Both questionnaires will be answered after this reflection period.

9.3 Variables

The following data will be collected from the patients' medical records and reported on the CRF by the investigator.

Consent

- Unique Study subject number (ISO three letter Country Code, followed by site number within country and consecutive patient number within site)
- Date of Informed Consent (dd.MMM.yyyy)
- Date of first case report recording (dd.MMM.yyyy)

Demographics

- Month/Year of Birth (MMM.yyyy)
- Gender (Male/Female)
- Weight (kg)
- Height (cm)

Medical History

- Date of diagnosis of psoriasis (dd.MMM.yyyy)
- Location of Psoriasis (List: scalp, nail, body, joint involvement, genital or intimate psoriasis, other)
- Body Surface Area (xx%)
- Commonly associated comorbidities (List: cardiovascular diseases, diabetes, hypertension, depression, psoriasis arthritis, inflammatory bowel disease, other)
- Smoking habits (never, active with pack years, not active with pack years and years since stopped)
- Alcohol consumption (never, occasionally or regularly with number of days/week, number of drinks per day when alcohol is used)
- Prior psoriasis treatment and posology + reason for discontinuation of the last therapy administered
- Standard occupational category.

Psoriasis treatments during study period

THIS DOCUMENT CONTAINS TRADE SECRETS, AND/OR COMMERCIAL OR FINANCIAL INFORMATION, PRIVILEGED OR CONFIDENTIAL, DELIVERED IN CONFIDENCE AND RELIANCE THAT SUCH INFORMATION WILL NOT BE COPIED OR MADE AVAILABLE TO ANY THIRD PARTY WITHOUT THE WRITTEN CONSENT OF LEO PHARMA A/S

- Study treatment & co-medications (product name, formulation, dose, number of prescribed packages, package size)
- Date of treatment initiation
- Date of discontinuation (dd.MMM.yyyy)
- Reason for discontinuation (noncompliance, adverse event, requirement for alternative therapy, death, pregnancy, other)

Severity/effectiveness

- Psoriasis area and severity index (PASI)

Patient Reported Outcome

- Dermatology Life Quality Index (DLQI) score
- PSO-TARGET QoL component grid

The collected data are presented in the following flow chart of the study :

THIS DOCUMENT CONTAINS TRADE SECRETS, AND/OR COMMERCIAL OR FINANCIAL INFORMATION, PRIVILEGED OR CONFIDENTIAL, DELIVERED IN CONFIDENCE AND RELIANCE THAT SUCH INFORMATION WILL NOT BE COPIED OR MADE AVAILABLE TO ANY THIRD PARTY WITHOUT THE WRITTEN CONSENT OF LEO PHARMA A/S

Reporter	Data to be collected	Base-line Visit (Day 0)	3 months Visit (week 12-16)	12 months visit (week 48-56)
Investigator	Unique Study subject	X		
	Month/Year of Birth	X		
	Gender	X		
	Weight	X		
	Height	X		
	Date of diagnosis	X		
	Location of Psoriasis	X		
	Body Surface Area	X		
	Commonly associated comorbidities	X	X	X
	Smoking habits	X		
	Alcohol consumption	X		
	Prior psoriasis treatment	X		
	Psoriasis treatment during study period	X	X	X
	Date of discontinuation of psoriasis treatment during study period		X	X
	Reason for discontinuation of psoriasis treatment during study period		X	X
Patient	PASI	X	X	X
	QoL component grid	X	X	X
Patient	DLQI	X	X	X
	PSO-TARGET QoL component grid	X	X	X

9.4 Data Source

Investigator will complete the CRF with assessments and information according to the protocol. In addition, participants (patients) will be asked to enter data about their psoriasis symptoms and their Quality of Life, during the data collection period.

The below described scores will be mandatory:

Psoriasis Area and Severity Index (PASI) is the most widely used tool for the measurement of severity of psoriasis in clinical research. PASI combines the assessment of the severity of lesions and the area affected into a single absolute score in the range 0 (no disease) to 72 (maximal disease).

The **Dermatology Quality of Life Index (DLQI)** is well recognized Quality of Life questionnaire in psoriasis and capture a combination of symptoms, impact on daily routines, and feeling of stigmatization. It is a simple 10-question validated questionnaire that has been used in over 40 different skin conditions in over 80 countries and is available in over 90 languages. Its use has been described in over 1000 publications including many multinational studies. It is recommended to provide indirect measure of disease severity and is well used in studies on psoriasis and mentioned in the UK-treatment guideline (for details, see section 9.1.3).

The **PSO-TARGET QoL component grid** is a novel tool designed using a retrospective survey based on the recollection and experience from 3 clinical dermatologists of patient's expectations. It contains 12 therapeutic goals equally distributed into the 4 major psychometric components classically used in quality of life studies in patients suffering from chronic diseases (Chassany, 2003; Forestier et al., 2019). These four dimensions are: physical, subjective, relational/social and therapeutic. It has never been used before since it was designed for the PSO-TARGET study. Each patient will be required to pick only one item in the grid as his/her main therapeutic goal (see section 9.1.2). Treatment satisfaction in regards to the chosen component will be assessed at 12/16 weeks and 52 weeks by a 4 points Likert Scale and the level of concordance will be compared to DLQI scoring classes (described in section 9.1.2).

9.5 Study Size

The main criterion is the sensitivity of the PSO-TARGET tool (percentage of patients who consider their target objective as being achieved after 12/16 weeks of treatment as defined by a "satisfied or very satisfied" response, assessed on a 4 points Likert scale, among patients with a DLQI total score of 0 or 1).

The sample size calculation is based on the following hypotheses:

Sensitivity: 90%

Absolute precision : 10%

Type I error : 5%

Power at 80%

Prevalence: 80% (estimated rate of patient with a DLQI 0-1 after 12 weeks of treatment)

Hypothesis :

THIS DOCUMENT CONTAINS TRADE SECRETS, AND/OR COMMERCIAL OR FINANCIAL INFORMATION, PRIVILEGED OR CONFIDENTIAL, DELIVERED IN CONFIDENCE AND RELIANCE THAT SUCH INFORMATION WILL NOT BE COPIED OR MADE AVAILABLE TO ANY THIRD PARTY WITHOUT THE WRITTEN CONSENT OF LEO PHARMA A/S

$H_0 : Se = Se_0$

$H_1 : Se = Se_1 > Se_0$

With Se =sensitivity, $Se_0=0.8$ and $Se_1=0.9$

Using the binomial probability formula, the sample size necessary to meet both a significance level and a power requirement may be found by solving the following two equations simultaneously :

Significance level $B(s_1 > s \alpha | n_1, Se_0) = \alpha$

$B(s_1 > s \alpha | n_1, Se_1) = 1 - \beta$

Where n_1 : patients with a DLQI 0-1, s_1 : patients with a DLQI 0-1 and a positive test outcome

With $\alpha=0.05$ and $1 - \beta=0.8$

To obtain n , n_1 is inflated by the prevalence P (rate of patients with a DLQI 0-1 = 80%), to obtain $n = n_1 / P$

The software used is PASS version 12, using the Li and Fine method (Li and Fine, 2004).

Based on these hypotheses, the sample size needed is estimated at 134 evaluable patients.

Assuming 10% of patients will not be evaluable on main criterion, **150 patients have to be included.**

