QoL component grid. True Positive (TP), False Positive (FP), True Negative (TN) and False Negative (FN) will be defined using a contingency table. These quantitative variables will be used to calculate the sensitivity (proportion of actual satisfied patients that are correctly identified as such) and specificity (proportion of actual unsatisfied patients that are correctly identified as such) of the PSO-TARGET QoL Component grid, compared to the quality of life given by the DLQI. If these metrics reach a certain threshold (85%), the PSO-TARGET QoL component grid will be considered for additional studies in order to validate it at a larger scale and further demonstrate it is as much sound in assessing the patients' quality of life as the DLQI.

Because of the fact that alexithymia is highly prevalent in psoriasis patients, the grid will be administered to the patient after he/she had spontaneously expressed his/her treatment expectations. This should help the patient to narrow down the specific goal where his/her expectation belongs. In addition, as part of a secondary objective the treating physician will also choose an item from the table based on what he/she perceives in terms of patient's expectations without disclosing it to the patient. This will allow us to evaluate the level of accordance between the physician-chosen and the patient-chosen therapeutic goal. As another secondary endpoint, the level of achievement of the therapeutic goal will be assessed at 12/16 weeks and followed-up for 52 ± 4 weeks. Patients scoring the treatment as "satisfied or very satisfied" will be considered as having achieved their therapeutic goal. Another endpoint of interest (secondary) will be to assess, after 12/16 weeks of treatment, if the patient chooses a new therapeutic goal, different from the one he initially defined.

It is important to note that, this study being observational, none of the visits (baseline and follow-ups) are specific to the trial but part of the dermatologists' standard of care in both countries (France and Belgium). In addition, in order to limit variability in terms of treatment profiles (dosage and administration schedule) and thus to keep the study population as homogenous as possible, it has been decided to include only patients treated by Kyntheum®, in other terms Kyntheum® treatment is an accessory to the study but PSO-TARGET will not assess Kyntheum® efficacy *per se*.

The study objectives are the following:

Primary objective:

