THIS DOCUMENT CONTAINS TRADE SECRETS, AND/OR COMMERCIAL OR FINANCIAL INFORMATION, PRIVILEGED OR CONFIDENTIAL, DELIVERED IN CONFIDENCE AND RELIANCE THAT SUCH INFORMATION WILL NOT BE COPIED OR MADE AVAILABLE TO ANY THIRD PARTY WITHOUT THE WRITTEN CONSENT OF LEO PHARMA A/S

baseline. The therapeutic objective achievement is defined as “satisfied” or “very satisfied” response on 4 points Likert scale.

- Level of concordance between the satisfaction level in regard to the therapeutic objective set by the PSO-TARGET QoL Component grid and the DLQI at the 2nd follow-up visit (52 ± 4 weeks.).
- Research of predictive factors (among baseline characteristics) of the achievement of the main treatment goal.
- Percentage of agreement between the physician-reported and the patient-reported dimensions at the first follow-up visit.
- Rate of patients having changed objective at the 1st follow-up visit (12/ 16 weeks).
- Percentage of patients who have maintained at 52 ± 4 weeks the level of satisfaction achieved at the 1st follow-up visit.
- PASI Scores at baseline, at the 1st follow-up visit (12/ 16 weeks), at the 2nd follow-up visit (52 ± 4 weeks.).
- Level of accordance between PASI 90/100 and the satisfaction level in regard to the therapeutic objective set by the PSO-TARGET QoL Component grid.
- DLQI Scores at baseline, at the 1st follow-up visit (12/ 16 weeks), at the 2nd follow-up visit 52 ± 4 weeks.

Data sources

Patients' data will be collected at day 0, at the 1st follow-up visit (12/16weeks) and at the 2nd follow-up visit at 52 ± 4 weeks according to the physician's practice.

As a prospective study, the following data will be collected during the patient visit: disease history, concomitant treatments, previous anti psoriatic treatment and adverse events. In addition, the following study specific data will be collected: disease severity (PASI score), quality of life questionnaires (DLQI, PSO-TARGET component grid).

Study size

The main criterion is the sensitivity of the PSO-TARGET tool (percentage of patients who consider their target objective as being achieved after 12/16 weeks of treatment as defined by a “satisfied or very satisfied” response, assessed on a 4 points Likert scale, among patients with a DLQI total score of 0 or 1).

The sample size calculation is based on the following hypotheses :

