THIS DOCUMENT CONTAINS TRADE SECRETS, AND/OR COMMERCIAL OR FINANCIAL INFORMATION, PRIVILEGED OR CONFIDENTIAL, DELIVERED IN CONFIDENCE AND RELIANCE THAT SUCH INFORMATION WILL NOT BE COPIED OR MADE AVAILABLE TO ANY THIRD PARTY WITHOUT THE WRITTEN CONSENT OF LEO PHARMA A/S

- ✓ Sensitivity : 90%
- ✓ Absolute precision : 10%
- ✓ Type I error : 5%
- ✓ Power at 80%
- ✓ Prevalence: 80% (estimated rate of patients with a DLQI 0-1 after 12 weeks of treatment.

Based on these hypotheses, the sample size needed is estimated at 134 evaluable patients.

Assuming 10% of patients will not be evaluable on main criterion, **150 patients have to be included.**

Data analysis

Analysis of the primary endpoint

The performance of the PSO-TARGET QoL component grid to assess the treatment impact on the patients' quality of life will be determined by calculating the sensitivity and specificity of the grid compared to the DLQI (reference). The grid will be validated if both the specificity and sensitivity parameters reach the 85% threshold.

Milestones

Regulatory Submissions: Q2 2020

Start of data collection Q3 2020

End of data collection Q2 2022

Final report Q4 2022

5 Amendments and Updates

None

THIS DOCUMENT CONTAINS TRADE SECRETS, AND/OR COMMERCIAL OR FINANCIAL INFORMATION, PRIVILEGED OR CONFIDENTIAL, DELIVERED IN CONFIDENCE AND RELIANCE THAT SUCH INFORMATION WILL NOT BE COPIED OR MADE AVAILABLE TO ANY THIRD PARTY WITHOUT THE WRITTEN CONSENT OF LEO PHARMA A/S

6 Milestones

Planned dates for study milestones are indicated in the table below:

Milestone	Planned Date
Start of data collection	Q3 2020
End of data collection	Q2 2022
Final study report	Q4 2022

The start of the study is defined as the date on which the first information on a study patient is recorded in the study dataset. LEO will ensure that End-of-Data Collection (End of Study) notification is submitted to the concerned authorities and IECs for each site, for each country and for the complete study.

Based on upcoming knowledge, LEO might choose to terminate the study prematurely. In such case the Committee(s), study sites, IECs and authorities will be informed promptly.

7 Rationale and Background

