
level of concordance of this satisfaction level and the overall quality of life as defined by the DLQI at the same time point. It is important to consider that systemic treatment by Kyntheum® is an accessory to the study but the objective of the PSO-TARGET is not to evaluate Kyntheum® efficacy.

As part of secondary objectives, in parallel to that initial assessment by the patient, the physician will tick on the grid what would be his patients therapeutic goal based on what he knows/understands from the patient's disease history and therapeutic desires. At the time of his/her assessment, the physician will be blinded of the patient's choice of therapeutic goal. The accordance between the physician-chosen and the patient-chosen dimensions will be analyzed. The 12 items of the tool will be pooled and analysed by component (physical, subjective, relational and therapeutic). At 52 weeks, among other secondary endpoints, the maintenance of the level of achievement of the initial objective observed at the 1st follow-up visit, will be assessed.

One of the innovative aspects of this exploratory observational study will be the administration of a psoriasis-specific quality of life component grid containing 12 treatment objectives grouped in the 4 quality of life components/dimensions usually impacted in patients suffering from chronic diseases (Chassany, 2003; Forestier et al., 2019). Those dimensions accounting for the burden to bear when suffering from a chronic disease are the following: Physical, Subjective, Relational/Social and Therapeutic. Each dimension will include 3 patient's therapeutic goal based on dermatologists' clinical experience and reviewed by an expert on psychometric tools.

This is an exploratory study, a first step to assess the interest of the PSO-TARGET component grid. If the sensitivity and specificity reach an acceptable threshold (85%), the potential of the PSO-TARGET grid will be considered for validation in larger clinical studies. Indeed, more studies will be needed to test other attributes in order to fully validate the PSO-TARGET grid as an alternative to the DLQI for QoL assessment. Once the PSO-TARGET component grid is validated, it will prove to be a useful tool for a better design of a therapeutic objective from the physician and thus a better care brought to the patient which should improve the patient's satisfaction and treatment adherence.

8 Research Question and Objectives

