8.1 Primary Objective

The primary endpoint will be the evaluation at week 12/16 of the sensitivity and the specificity, compared to the DLQI as a standard, of the PSO-TARGET QoL component grid to assess the level of satisfaction of patient achieving the therapeutic goal, identified by himself.

The therapeutic objective will be considered as achieved if the patient gives the responses "Satisfied" or "Very Satisfied" on the Likert scale. The response will then be compared to the DLQI score at 12/16 weeks.

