9.8.3 Sensitivity/sensibility analysis

- Analysis of the primary endpoint

The primary endpoint will be the evaluation at week 12/16 of the sensitivity and the specificity, compared to the DLQI as a standard, of the PSO-TARGET QoL component grid to assess the level of satisfaction of patient achieving the therapeutic goal, identified by himself.

The therapeutic objective will be considered as achieved if the patient gives the responses “Satisfied” or “Very Satisfied” on the Likert scale. The response will then be compared to the DLQI score at 12/16 weeks.

It will be described on the efficacy population.

A contingency table will be constructed as follows:

PSO-TARGET \ DLQI	0-1	2-5	6-10	11-20	21-30
Very satisfied	TP	FP	FP	FP	FP
Satisfied	TP	FP	FP	FP	FP
Unsatisfied	FN	TN	TN	TN	TN
Very unsatisfied	FN	TN	TN	TN	TN

This table can be summarized as :

PSO-TARGET \ DLQI	0-1	≥ 2
Very satisfied ou Satisfied	TP	FP
Unsatisfied ou Very unsatisfied	FN	TN

TP: True positive

FP: False Positive

FN: False Negative

TN: True Negative

The validity of the QoL component grid will then be assessed by calculating the following parameters:

Sensitivity: defined as the probability to have patients who have reached their therapeutic target (who have responded « satisfied » or « very satisfied » on the Likert scale, globally and in each major domains) among patients with a DLQI score between 0 and 1.

In other terms the sensitivity is defined as the **concordance** of the QoL component grid and the DLQI **for the patients with optimal quality of life**.

The sensitivity is calculated by:

$$Se = \frac{TP}{TP + FN}$$

Specificity: defined as the probability to have patients who have not reached their therapeutic target (who have responded « unsatisfied » or « very unsatisfied » on the Likert scale, globally and in each major domains) among patients with a DLQI score ≥2.

In other terms the specificity is defined as the **concordance** of the QoL component grid and the DLQI **for the patients with suboptimal quality of life**.

The specificity is calculated by:

$$Sp = \frac{TN}{FP + TN}$$

The QoL component grid will be validated if these two parameters reach the threshold of 85%.

THIS DOCUMENT CONTAINS TRADE SECRETS, AND/OR COMMERCIAL OR FINANCIAL INFORMATION, PRIVILEGED OR CONFIDENTIAL, DELIVERED IN CONFIDENCE AND RELIANCE THAT SUCH INFORMATION WILL NOT BE COPIED OR MADE AVAILABLE TO ANY THIRD PARTY WITHOUT THE WRITTEN CONSENT OF LEO PHARMA A/S

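### The sample size and 80% power are for sensitivity alone, but the grid is validated only if sensitivity and specificity both reach 85%, and specificity rests on about 27 patients

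*Protocol*

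**What the plan says.** The protocol describes its principal quantity in two ways.

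- **Sizing.** Section 9.5 says "The main criterion is the sensitivity of the PSO-TARGET tool", meaning the share of patients answering satisfied or very satisfied among those with DLQI 0 or 1. The abstract's study size uses the same words. The hypotheses in 9.5 are Se0 = 0.80 against Se1 = 0.90, with 5% type I error, 80% power and an 80% prevalence of DLQI 0-1. The result is 134 evaluable patients and 150 included. Neither specificity nor the 85% threshold enters this calculation.
- **Decision.** Section 8.1 says "The primary endpoint will be the evaluation at week 12/16 of the sensitivity and the specificity, compared to the DLQI as a standard". The abstract's data analysis says "The grid will be validated if both the specificity and sensitivity parameters reach the 85% threshold", and section 9.8.3 repeats the rule: "The QoL component grid will be validated if these two parameters reach the threshold of 85" per cent. Specificity is computed among patients with DLQI ≥ 2.
- **Consequence of a pass.** The abstract says "If these metrics reach a certain threshold (85%), the PSO-TARGET QoL component grid will be considered for additional studies". Section 7 is equally modest: "the potential of the PSO-TARGET grid will be considered for validation in larger clinical studies".

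**The concern.** A power statement should describe the decision the study will make. Here it describes a significance test of sensitivity against 80%, while the decision compares sensitivity and specificity with 85%. The stated 80% is therefore the success probability of neither the joint rule nor its sensitivity half.

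Specificity cannot pass the grid alone, but it can fail it alone. It rests on about a quarter as many patients as sensitivity (27 against 107), so the two halves do not discriminate equally well just below the threshold. Someone who reads the 80% as the chance of reaching the validation decision would be relying on a figure that was never calculated.

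**Working it through.** **Inputs from the protocol.** Se0 = 0.80, Se1 = 0.90, alpha 5%, power 80%, prevalence of DLQI 0-1 80%, N = 134 (all section 9.5); two-tailed testing (9.8); both parameters at 85%, with specificity among DLQI ≥ 2 (9.8.3).

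**Assumptions.** Reaching 85% is taken to mean the point estimate, since the protocol does not tie it to a confidence limit. True specificity is not given, so a range is shown.

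**1. The plan's own figure.** Exact binomial test, upper tail 0.025:
- At n1 = 107 the critical count is 94: P(X ≥ 94 | 107, 0.80) = 0.0233 and P(X ≥ 94 | 107, 0.90) = 0.819.
- This is the first n1 with power of at least 80%. Then 107 / 0.80 = 133.75, rounded up to 134.
- A one-sided 5% test would give n1 = 82 and N = 103, so the plan used two-sided 5%.

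The 134 reproduces.

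**2. What the validation rule requires.**
- Sensitivity: 0.85 × 107 = 90.95, so at least 91/107, not 94/107. A true 0.90 meets this with probability 0.963 at n1 = 107.
- Specificity: expected n0 = 0.20 × 134 = 26.8, about 27; the 2.5% and 97.5% points of Bin(134, 0.20) are 18 and 36. With 27 patients, 0.85 × 27 = 22.95, so at least 23/27.

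**3. Chance of passing.** For each split, the pass probability is P(X ≥ ⌈0.85n⌉ | n, p). It is averaged over n1 ~ Bin(134, 0.80) with n0 = 134 − n1, because results at a fixed n0 jump with discreteness (a specificity of 0.80 passes 0.207 at n0 = 26, 0.348 at 27 and 0.255 at 30).

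| True value | Sensitivity half | Specificity half |
|---|---|---|
| 0.90 | 0.951 | 0.813 |
| 0.80 | 0.096 | 0.277 |

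| True Se / Sp | Joint pass |
|---|---|
| 0.90 / 0.95 | 0.930 |
| 0.90 / 0.90 | 0.773 |
| 0.90 / 0.85 | 0.505 |
| 0.90 / 0.80 | 0.263 |
| 0.80 / 0.90 | 0.078 |
| 0.80 / 0.80 | 0.026 |

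**4. Range for prevalence.**

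| Prevalence of DLQI 0-1 | Joint pass, 0.90/0.90 | Sp 0.80 passes its half | Se 0.80 passes its half | Ratio |
|---|---|---|---|---|
| 70% | 0.804 | 0.226 | 0.112 | 2.0 |
| 80% | 0.773 | 0.277 | 0.096 | 2.9 |
| 90% | 0.715 | 0.349 | 0.084 | 4.2 |

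**5. Precision (exact Clopper-Pearson 95%).** A bare pass of 23/27 gives 66% to 96%. Mean limits at a true 0.90:
- n = 18: 67% to 98%
- n = 27: 73% to 98%
- n = 36: 76% to 97%
- n = 107 (sensitivity): 83% to 95%

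**6. Range for the point-estimate assumption.** If the exact lower 95% limit had to reach 85%, the requirement would be 99/107 and 27/27 (26/27 has a lower limit of 81%). The averaged joint pass at 0.90/0.90 would be 0.013.

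**The case against.** The strongest reply is that little follows in practice.

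- **The joint figure is close to 80%.** It is 77% at 0.90/0.90. This stands only if true specificity is near 0.90, which the protocol never assumes; at 0.80 the figure is 26%.
- **A clearly poor grid is still stopped.** With sensitivity 0.90 and 80% prevalence, the joint pass is about 4% at specificity 0.70 and 0.4% at 0.60 (about 11% and 3% at 90% prevalence). This stands: the weakness lies mainly just below the threshold.
- **The sensitivity half is well served.** Any result that passes 94/107 also passes 91/107, so the stated power is a conservative bound for that half. This is also right, but it confirms that the 80% is not the probability of the decision.
- **Section 9.5 is open that its hypotheses concern sensitivity.** True, and sizing on one parameter is permissible if disclosed. What remains wrong is naming that parameter alone as the main criterion when 8.1 and 9.8.3 use two.
- **The study is exploratory.** Correct, and it limits the harm. The abstract's data analysis and 9.8.3 nevertheless attach validation to this rule.
- **Confidence intervals belong to the SAP.** In part. Section 9.8 makes them optional, however, and the protocol itself fixes the 85% rule they would qualify.

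**Conclusion.** The concern holds. The arithmetic behind 134 is sound, but the sizing and the decision rule address different questions, and the main criterion is stated inconsistently. At the protocol's 80% prevalence, specificity rests on about 27 patients (18 to 36). A true specificity of 0.80 passes its half about three times as often as a true sensitivity of 0.80 passes the other (two to four times for prevalence 70% to 90%). The probability of the actual decision runs from 26% to 93% for specificity 0.80 to 0.95 with sensitivity 0.90.

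These figures rest on the point-estimate reading of 85% and on assumed specificities. The lower-limit reading would make the rule almost impossible to pass, but it is not the natural one and the conclusion does not depend on it. This should be fixed; because the study is exploratory, corrected wording is enough.

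**What to change.** Amend the abstract's study size and sections 9.5 and 9.8.3 as follows.

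1. State that the 80% power is for the test of sensitivity 0.80 against 0.90 only, and not for the decision requiring both parameters at 85%.
2. Reconcile the main criterion with 8.1 and 9.8.3, which use both parameters.
3. Give the expected number with DLQI ≥ 2 (about 27 of 134) and the resulting precision of specificity. As an illustration at an assumed true specificity of 0.90, this is about 73% to 98%, and the joint rule passes about 77% of the time when both parameters are 0.90. Mark the 0.90 for specificity as an assumption.
4. Report both parameters with exact 95% confidence intervals wherever the 85% rule is applied.

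The cost is a few sentences and an open admission that specificity will be imprecise. No patients or visits are added.
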